Definitions will be implemented as described in section 9.3 Variables. Patients who are known to be alive at the date of data collection (1-year for interim report and 3-year for full study report) will be censored at the date of data collection, and patients who are lost to follow-up will be censored on the date they were last known to be alive (e.g. date of last recorded hospital visit). Patients who are alive and free from disease progression at the date of data collection and those lost to follow-up will be censored on the date they were last known not to have disease progression (i.e. the date of last documented response assessment). Patients remaining in CR or PR at the end of the post-initiation observation period or lost to follow-up will be censored on the date CR or PR was last documented.

For the estimation of the proportion of patients alive, and free from disease progression, the denominator will be all patients known to be alive at the selected time-points (1 years, 2 years and 3 years). For the estimation of the proportion of patients achieving PR, CR and with stable disease at the selected time-points (1 years, 2 years and 3 years), the denominator will be all patients with at least one assessment of response (CR / PR / no response or stable disease / progressive disease) in the past year. Estimation of time to achieving best overall response and duration of response; and representation using swimmer plots will be performed in patients who respond (achieve CR or PR during follow-up) only.

Median PFS, OS, time to achieving best overall response, time to palbociclib dose modification and time to palbociclib discontinuation, and corresponding 95% CIs, will be estimated using Kaplan-Meier curves. Assessments of response (CR / PR / no response or stable disease / progressive disease) in patients responding to treatment (achieving CR or PR following initiation of palbociclib) will be represented using “swimmer plots”.

All percentages will be reported to the nearest whole number; therefore, in reporting study results in tables, figures and associated text, percentages may not add up to 100% due to rounding.

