9.9. Limitations of the research methods

- Comparisons of the results of this study with that of clinical trials and other real-world studies may be limited due to the presence of several potential sources of bias.
- Several sources of selection bias may be introduced in the study:

- At sites where data are collected by pH Associates, consent from living patients will be required; and consequently a low rate of consent amongst living patients may introduce an over-representation of deceased patients (for whom consent is not required) at those sites, and also compared to sites where consent is not required as all data are collected by the direct medical care team.
- Patients were treated as part of routine care and therefore patients enrolled in this study may have more diverse characteristics than in a clinical trial setting (for example with regard to menopausal status, ER and PR status, HER2 status), which may impact on the efficacy of palbociclib.
- Patients will be recruited from larger centres enrolled in the IPP, which may differ from smaller centres in terms of demographic and clinical characteristics, and therefore may not be representative of all patients treated with palbociclib in routine care as part of the IPP.
- Patients may be lost to follow-up due to the occurrence of AEs, lack of efficacy or other reasons, introducing attrition bias. However, the use of Kaplan-Meier curves will be used to obtain estimates of median PFS OS, CR, PR and this takes into account patient attrition.
- Radiological results will be collected from medical notes recorded by radiologists who were unblended to patient's treatment, introducing potential measurement bias.
- The interpretation of data collected retrospectively will be dependent on the completeness and quality of the medical records and the reliability of the abstraction of data from the medical records. However, SDV will be employed to identify and correct abstraction errors.
- This is a descriptive study and no analyses to control for confounding will be carried out; therefore, no definitive causal relationships between Ibrance® and study endpoints can be made.
- At sites where data are collected by pH Associates, a low consent rate may diminish sample size and the target of 250 patients enrolled into the study may not be achieved. If <200 patients are recruited into the study, an expansion of the study to other sites involved in the IPP will be considered.

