2.1 STUDY DESIGN

This study will be a UK-wide, multi-centre, non-interventional cohort study (Figure 1). The study will involve secondary use of hospital medical records (paper-based or electronic, as appropriate), collected both retrospectively and prospectively, from patients' medical records. Data will be collected for a maximum of 3 years following enrolment into the IPP.

The palbociclib initiation date will be defined as the index date. The baseline period will extend from the date of diagnosis up to palbociclib initiation (index date). The post-initiation observation period will be defined as the period from the index date until the end of the 3-year follow-up period. Patients will contribute data up to the time that they are lost to follow-up (for example due to discharge, death, or other reasons) or 3-year post-index observation period, whichever is sooner.

PFIZER CONFIDENTIAL

[figure not shown]
[figure not shown]

Figure 1. Schematic of study design**Study population**

Across the entire UK, 846 women received palbociclib as part of the IPP. In the sites selected for this study, approximately 200 patients received palbociclib as part of the IPP and consented to participate in the study.

All patients meeting the following eligibility criteria will be included in the study:

- Patients enrolled into the IPP at one of the selected sites.
- Patients who received ≥ 1 dose of palbociclib as part of the IPP at one of the selected sites.
- For sites where data collection is performed by pH Associates, written informed consent will be required from living patients to access their medical records.
- Patient aged ≥ 18 years old at enrolment into the IPP

All eligible patients within the selected sites will be recruited into the study (and who provide informed consent, in the case of living patients, at sites where data collection is performed by pH Associates).

Data will be retrospectively collected from the point of patient's enrolment into the IPP until initial data collection, expected to take place between November 2018 and February 2019. After the initial retrospective data collection, data will be collected prospectively up to a maximum of 3 years from enrolment in the IPP by members of the direct care team by updating the eCRF with any subsequent therapeutic and progression data available in the medical records until the end of the 3-year follow-up period.

PFIZER CONFIDENTIAL

Data source

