7 HANDLING OF MISSING VALUES

Where dates are ambiguous because of missing day and/or months, standard imputation will be applied: where day is missing the 15th of the month will be assumed; where both day and month are missing the 1st of July will be assumed unless data collected is in 2017 (year of initiation of IPP) in which case the 15th of August will be assumed (midpoint as IPP was initiated in April 2017). The 15th of August will only be used for missing dates that are related to the IPP program, e.g., start date of palbociclib cycle. Where other types of data are missing from the original medical record, the affected analyses will be conducted using only the results of those patients with data available and the number included in each analysis will be stated. The percentage of data missing will be reported for each study variable. The calculation of percentages will not contain the missing categories. Counts of missing observations will be presented in a separate category.

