Proposed: Starting and mean dose of palbociclib and subsequent treatments after progression, length of treatments and time to dose reduction and discontinuation of palbociclib in days will be summarised as quantitative variables (see section 8.1.1). Times will be calculated in days through subtracting the time of first dose reduction/discontinuation from the date of palbociclib initiation. Treatment after progression and reasons for discontinuation, the proportion of patients completing a daily cycle, having dose reductions, treatment discontinuation and being co-administered letrozole and fulvestrant at palbociclib initiation will be summarised as categorical variables using frequencies and percentages (see section 8.1.2). Reasons for discontinuation of palbociclib will be presented as categorical data (see section 8.1.2) The proportions of patients with dose reductions and discontinuation will be calculated separately at 1 and 2 years after palbociclib initiation. Quantitative discrete variables (such as the number of completed cycles per patient) will be summarised using a combination of the approaches described in sections 8.1.1 and 8.1.2, if appropriate.

Actual: Starting dose of palbociclib was presented as a categoric variable as per section 8.1.2. Endocrine partner prescribed alongside palbociclib, proportion of patients with recorded dose reductions, proportion of patients who discontinued palbociclib and the associate reasons, proportion of patients with temporary interruptions to palbociclib treatment were presented as categoric variables as per section 8.1.2. Time to dose reduction was presented as a categoric variable as per section 8.1.2 (Categories: Patient did not have a dose reduction, dose reduction occurred within 3 months of palbociclib initiation, dose reduction occurred between 3 and 6 months after palbociclib initiation and dose reduction occurred over 6 months after palbociclib initiation). Number of patients

PFIZER CONFIDENTIAL

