8.2.9 Summary of Analyses

Outcome	Analysis Set	Supports Protocol Objective Number	Subgroups	Statistical Method	Missing Data
Summary of age at initiation of palbociclib	Full Analysis set	Primary Objective	Overall and treatment Line	Calculated by subtracting Date of palbociclib initiation from Date of Birth. Summary statistics calculated (incl. Mean/Median/SD/IQR/Range)	Day of birth assumed to be the 15 th . If month is missing, birthday assumed to be 1 st July. Otherwise excluded.
Distributions of categorical, binary, and ordinal demographical and clinical characteristics	Full Analysis set	Primary Objective	Overall and treatment Line	Frequency tables and percentages	Excluded
Summary measures of MBC statistics	Full Analysis set	Primary Objective	Overall and Treatment Line	Frequency tables and percentages Summary statistics for Ki67 proliferation index (incl. Mean/Median/SD/IQR/Range)	Excluded
Duration of MBC at palbociclib initiation	Full Analysis set	Primary Objective	Overall and Treatment Line	Calculated by subtracting Date of palbociclib initiation from Date of MBC diagnosis. Summary statistics calculated (incl. Mean/Median/SD/IQR/Range)	Standard imputation for dates (section 7), otherwise exclude.
Treatment for MBC diagnosis prior to palbociclib initiation	Full Analysis set	Primary Objective	Overall and Treatment Line	Frequency tables and percentages	Excluded
Summaries of comorbidities and Charlson comorbidity index of patients at palbociclib initiation	Full Analysis set	Primary Objective	Overall and Treatment Line	Frequency tables and percentages for each comorbidity type Summary statistics calculated (incl. Mean/Median/SD/IQR/Range) for Charlson comorbidity index	Excluded
Palbociclib prescribed as on or off-label	Full Analysis set	Primary Objective	Overall and Treatment Line	Frequency tables and percentages	Excluded
Summary measures of palbociclib treatment patterns	Full Analysis set	Secondary Objective 1	Overall and Treatment Line	Frequency tables and percentages for proportions and categorical variables such as proportion of patients with dose reductions or discontinuation and reasons for discontinuation Summary statistics calculated (incl.	Excluded

PFIZER CONFIDENTIAL

				Mean/Median/SD/IQR/Range) for doses, time to dose reduction and discontinuation and length of treatment	

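### The 1- and 2-year proportions with palbociclib dose reduction and discontinuation are crude percentages, with no rule for patients whose follow-up ends event-free before the landmark

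*SAP*

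**What the plan says.** The Proposed text of SAP 8.2.2 (Secondary Objective 1) fixes the landmarks: "The proportions of patients with dose reductions and discontinuation will be calculated separately at 1 and 2 years after palbociclib initiation". It also fixes the method, the categorical route of SAP 8.1.2: "having dose reductions, treatment discontinuation and being co-administered letrozole and fulvestrant at palbociclib initiation will be summarised as categorical variables using frequencies and percentages". The treatment-pattern row of SAP 8.2.9 repeats it: "Frequency tables and percentages for proportions and categorical variables such as proportion of patients with dose reductions or discontinuation". That row names the Full Analysis Set and lists missing data as excluded.

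The Actual text of 8.2.2 again uses the categorical route, for the "proportion of patients with recorded dose reductions, proportion of patients who discontinued palbociclib and the associate reasons". It names no landmark and no denominator. SAP 6 still lists a 3-year landmark, although the analysis is limited to 2-year data.

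The general missing-data rule in SAP 7 is that "the affected analyses will be conducted using only the results of those patients with data available". It does not say whether a patient whose follow-up stops early counts as having data available.

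Both documents expect incomplete follow-up. SAP 2.1: "Patients will contribute data up to the time that they are lost to follow-up". Protocol 9.9: "Patients may be lost to follow-up due to the occurrence of AEs, lack of efficacy or other reasons, introducing attrition bias".

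For the related times, Protocol 9.7 says that "time to palbociclib dose modification and time to palbociclib discontinuation, and corresponding 95% CIs, will be estimated using Kaplan-Meier curves". SAP 8.2.2 does not carry this through. Its Proposed text summarises the times as ordinary quantitative variables, SAP 6 restricts time to discontinuation to patients who stopped permanently, and the Actual text reports time to dose reduction in categories.

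**The concern.** A simple percentage at a fixed landmark estimates the proportion with the event by that time only if every patient is observed to the event or the landmark. A patient lost at month 8 on an unreduced dose has an unknown 2-year status, and the plan does not say where that patient goes.

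The gap is specific to these outputs. SAP 8.2.3 gives denominators for the alive, progression-free and response proportions, and the opening of SAP 8.2 gives censoring rules for survival, progression and response. Neither covers dose reduction or discontinuation.

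Both proportions are named outputs of Secondary Objective 1. As written, the 2-year values depend partly on how many patients were lost and how the analyst classified them, and no confidence interval is planned for them. If loss differs between the treatment-line subgroups of SAP 5.4, so may the distortion.

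**Working it through.** The plan states no loss rate and no expected proportion for either event, so there is no figure of its own to reproduce. The check asks how far the crude percentage can move.

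**Potential follow-up.** Index dates run from April to December 2017 (SAP 2) and collection was planned to February 2021 (Protocol 6). The latest index date plus 24 months is December 2019, so the planned calendar truncates nobody before 2 years. Only actual loss matters.

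**Inputs.**
- Time to discontinuation: exponential, median *M* = 20.2 or 24.8 months. These are the palbociclib-arm progression-free survival medians in Protocol 7, used as a proxy for time on drug (assumption).
- Loss by 24 months: *L* = 5%, 10% or 20%, exponential and independent of the event (assumption).
- Dose reduction: 33% by 12 months, the midpoint of the 32-34% that Protocol 7 cites from a US study, with discontinuation competing at *M* = 24.8 (assumption).

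**Formulas**, with λ = ln 2 / *M* and γ = -ln(1 - *L*) / 24:
- True proportion at *t*: 1 - exp(-λ*t*).
- (a) Lost patients kept as event-free: *A* = λ/(λ+γ) × [1 - exp(-(λ+γ)*t*)].
- Lost before *t* without the event: *C* = γ/(λ+γ) × [1 - exp(-(λ+γ)*t*)].
- (b) Only lost non-events dropped: *A* / (1 - *C*).
- (c) Everyone lost before *t* dropped, with or without an event: equals the true value when loss is independent.

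**One case in full** (*M* = 24.8, *L* = 10%, *t* = 24). λ = 0.02795, γ = 0.00439, sum 0.03234; 1 - exp(-0.03234 × 24) = 0.540. True = 48.9%. *A* = 0.864 × 0.540 = 46.7%. *C* = 0.136 × 0.540 = 7.3%. (b) = 46.7 / 92.7 = 50.3%.

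**Discontinuation at 2 years:**

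| *M* (months) | *L* | True | (a) kept as event-free | (b) lost non-events dropped |
|---|---|---|---|---|
| 20.2 | 5% | 56.1% | 54.9% (-1.2) | 56.8% (+0.7) |
| 20.2 | 10% | 56.1% | 53.6% (-2.5) | 57.6% (+1.5) |
| 20.2 | 20% | 56.1% | 51.1% (-5.1) | 59.3% (+3.1) |
| 24.8 | 5% | 48.9% | 47.8% (-1.1) | 49.6% (+0.7) |
| 24.8 | 10% | 48.9% | 46.7% (-2.2) | 50.3% (+1.5) |
| 24.8 | 20% | 48.9% | 44.3% (-4.5) | 52.0% (+3.1) |

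Handlings (a) and (b) differ by about 4 points at 10% loss and about 8 at 20%. At 1 year the largest shift is -1.7 points (*M* = 20.2, *L* = 20%). At *L* = 0 every shift is zero.

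**Dose reduction.** Solving λr/(λr+λ) × [1 - exp(-12(λr+λ))] = 0.33 gives λr = 0.0403 per month and a true 2-year cumulative incidence of 47.6%. At 5/10/20% loss, (a) gives 46.7/45.8/43.9% (-0.9/-1.8/-3.7) and (b) gives 47.9/48.2/48.8% (+0.3/+0.6/+1.3).

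**The wrong repair.** For dose reduction, 1 minus Kaplan-Meier with censoring at discontinuation gives 1 - exp(-λr*t*): 38.3% at 1 year and 62.0% at 2 years, against 33.0% and 47.6%. That error exceeds the crude percentage's error at every loss rate above.

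**Scale.** 1.96 × √[0.489 × 0.511 / *N*] is 6.9 points at *N* = 200 and 6.2 points at *N* = 250, the approximate sizes in SAP 2.1 and SAP 5.

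**The case against.** A reader might infer that the plan counts lost patients as still on treatment and unreduced, or drops them, and that both figures are therefore biased. The documents do not support that. They never say how such patients are classified, and the exclusion entry in 8.2.9 is a generic one on a row that also covers doses, times and treatment length. SAP 7 could even be read as dropping every patient lost before the landmark, which is unbiased under independent loss. Loss after discontinuation cannot affect the discontinuation figure.

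Nor do known deaths create bias. With no loss, cumulative incidence with death competing equals the crude percentage. What is missing for death is a definition: whether death on palbociclib counts as discontinuation.

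Three further points have force. The shifts at 5-10% loss (0.7 to 2.5 points for 2-year discontinuation) are well inside the sampling half-width, and Protocol 9.7 rounds percentages to whole numbers. Censoring also assumes non-informative loss, while Protocol 9.9 says loss may follow adverse events or lack of efficacy. And SAP 8.1.3 permits Kaplan-Meier proportions at time points for survival-related endpoints, though 8.2.2 does not invoke it.

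These points limit the size of the problem and of the gain. They do not supply the missing rule. Unlike sampling error, this bias does not shrink with more patients, and no interval is planned that would show either.

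**Conclusion.** The point holds in conditional form. The plan fixes a crude method for two named landmark outputs, expects patients to leave early, and gives no denominator or censoring rule for them. With loss before the landmark, the percentages are too low under handling (a) and too high under (b). They are unbiased with no loss, or under (c) with independent loss.

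At an assumed 5-20% loss by 24 months, 2-year discontinuation moves by about -1 to -5 points or +0.7 to +3 points. Dose reduction moves somewhat less, and 1-year figures by less than 2 points. These sizes rest on an assumed loss rate, exponential times, independent loss, and progression-free survival standing in for time on drug. The actual effect cannot be known from the documents. The change is worth making because it is cheap and gives the two outputs a defined meaning; the documents do not show that either figure is materially wrong.

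**What to change.** In SAP 8.2.2 and the matching row of 8.2.9, estimate both proportions at 12 and 24 months by cumulative incidence in the Full Analysis Set, with 95% confidence intervals.

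- **Discontinuation:** treat death on palbociclib as a competing event, or count it as end of treatment; state which.
- **Dose reduction:** treat permanent discontinuation or death before any reduction as competing events. Do not use 1 minus Kaplan-Meier censored at discontinuation.
- **Loss:** censor at the last recorded palbociclib status. Report the number at risk at each landmark and the number lost before it. State that the estimate still assumes loss unrelated to the event, which Protocol 9.9 questions.
- **Crude counts:** these may stay as a supplement, with the denominator and the handling of lost patients stated.

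The start, dose-change, end, death and last-visit dates are already in the dataset listed in the SAP appendix, so no new data are needed. Because 8.2.2 records these analyses as done, the cost is a modest re-analysis as well as SAP wording, and a slightly less simple table.
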